7.8.1 Drug storage

The BCG vaccine will be stored by Pharmacy under controlled ambient temperature. No additional temperature monitoring is required other than that required for general stock supplies held in the pharmacy for routine care. Please refer to the SmPC's for storage conditions for the BCG Vaccine.

7.8.2 Storage deviations

Storage including temperature monitoring of the drug will be as per the local trust guideline. In the event of excursions, local policies will be followed.

7.9 Accountability

Local pharmacy accountability logs will be completed in order to maintain traceability of the stock issued and returned within the trial.

7.10 Adherence

This is not applicable at the participant level since there is only a one-off dose administered by the site research team. The site research team will confirm on CRFs which participant's they administered the vaccine to once it has been given.

8. OUTCOME MEASURES

8.1 Internal pilot outcomes

An embedded internal pilot will run over a period of 9 months to assess site and participant recruitment and exclusion and primary outcome data completion.

The pilot outcomes are to:

Assess recruitment rate and exclusions: We aim for 20 sites enrolling at 9 months from study approval by the relevant authorities and target an overall recruitment rate of 1 patient per site per month. We will also examine reasons for non-inclusion of patients in the study; if high rates of exclusion occur due to patients declining, we will prioritise completion of qualitative acceptability work.

Assess primary outcome data completion: We aim for more than 90% of primary outcome data reported on the three month follow up form.

Assess an indication of the anticipated pooled AECOPD rate of the primary outcome: The pooled AECOPD rate at 3 months after date of treatment/randomisation will be used to indicate if the event rate is proceeding in line with what we would expect, such that the original sample size calculation remains accurate. The clinical adjudication committee will blindly review three-month AECOPD data collected directly from patients which will need confirmation via the routine care record (including data held on patient NHS App if necessary) at site, for the purposes of the 3-month review during the pilot. To meet the primary outcome of moderate to severe exacerbation, proof of antibiotic and/or steroid prescription (e.g. GP record of medication issue), and hospital admission (e.g. a discharge letter) respectively is required. Sites will be asked to confirm that such proof has been sent to be reviewed by the clinical adjudication committee.

We have considered Medical Research Council Hubs for Trials Methodology Research workshop guidance when determining stop/go criteria for the trial (43). Areas considered as suitable progression criteria include recruitment rate, protocol adherence (data completion) and outcome rate. A traffic

light system of green (go), amber (amend) and red (stop) was deemed preferable to a simple stop/go approach when specifying progression criteria for internal pilot studies, and they suggested recruitment progression criteria should be based on rates per centre per unit time that can be extrapolated, rather than specifying an absolute number by a specific date.

If sites overall have a recruitment rate of 1 participant per month, then recruitment will complete in 19-20 months across 50 sites. A recruitment rate of 1 participant/ month therefore represents green (go); if it is 0.5-0.9 participants/month this is amber (amend), and we will consider increasing the number of sites and enrolling patients after discharge from hospital due to an exacerbation, once 6 weeks have passed to allow stability; and if it is <0.5 participants/month this is red (stop).

	≥20 sites open for recruitment
Green	Sites overall recruitment rate of 1 participant per month (on average)
	>90% of primary outcome data reported on the three month follow up questionnaire
	5-19 sites open for recruitment
Amber	Sites overall recruitment rate of 0.5-0.9 participant per month (on average)
	80-90% of primary outcome data reported on the three month follow up form
	<5 sites open for recruitment
Red	Sites overall recruitment rate of <0.5 participants per month (on average)
	<80% of primary outcome data reported on the three month follow up form

Table 1 - Traffic light criteria

8.2 Main trial outcomes

8.2.1 Primary outcome(s)

The primary outcome is moderate to severe AECOPD rate over 12 months follow up from IMP administration date (or from the date of randomisation if no treatment was administered). This is defined by the clinical adjudication committee and will be based on an assessment of:

- basic patient details
- healthcare utilisation (taking additional antibiotics and/or steroids, as recorded in the medical record, including prescription data),
- patient-reported symptoms of the AECOPD
- laboratory results from patient-provided sputum, saliva, nose/throat swabs and DBS samples following an exacerbation

Severe events are defined by additional hospitalisation. Confirmation of events as stated in section 8.1, will occur via the CAC. Terms of reference for the CAC will be set.

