1.2.2 Justification for design

We have chosen a Prospective Randomised Open Blinded Endpoint (PROBE) design, powered to detect a 20% reduction, equivalent to 0.45 AECOPD/year in patients meeting our inclusion criteria. The primary outcome of the study is medically confirmed exacerbations of airways disease, treated with at least additional oral treatment (antibiotics or steroids); even though this moderate-severe AECOPD definition is a robust outcome commonly used in COPD trials, there is potential for bias to be introduced if the patient or clinician is aware they have received the vaccine. Despite the fact that a double blind design would be the most robust trial design with respect to bias, it have been proven to be exceedingly expensive and difficult to commercially produce matching blinded placebo vials. A PROBE study design maintains the benefits associated with a strict randomisation procedure, while the blinded end points help to eliminate bias. We will employ a group of clinical experts who are not responsible for recruiting participants into the trial to join an adjudication panel to determine the presence or absence of the exacerbation based on several sources of information. By doing this we will ensure that the primary outcome will be undertaken blinded to treatment allocation. Each panel

member will give their diagnosis and where there is disagreement, cases will be resolved by discussion. This addresses the problem of achieving a diagnosis from multiple sources of information and of subjective assessment of that information, as a diagnosis will be confirmed by consensus.

An alternative vaccine was not desirable as the trial concept is that non-specific immunity will be driven by BCG; another vaccine would only be an option if specific immunity were the outcome, or it was well known that an alternative vaccine did not have any non-specific immune priming, which is not the case.

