1.2.4 Justification of choice of primary outcome(s)

AECOPD are a significant burden to both the individual and the healthcare system and are not adequately controlled by existing therapies. Exacerbation reduction is also important to patients.

The primary outcome is moderate to severe AECOPD rate up to 12 months follow up. This is defined by healthcare utilisation (taking additional antibiotics and/or steroids, as recorded in the medical record, including prescription data), although we will collect symptom and treatment data from participants to infer if the event was infective. This will include all major and minor Anthonisen criteria (35), as well as whether antibiotics, steroids or antipyretics were taken.

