17.5 Sample Size

Tier 1 will consist of the whole cohort of 804 participants as for the main RCT.

Tier 2 will consist of the first 80 participants who have consented to provide samples for the detailed sub-study. Since consent to participate in the detailed mechanistic sub-study is a minimisation criterion, these 80 participants will be well balanced in terms of allocated treatment arm and the other minimisation criteria (see Section 6 – enrolment, randomisation and blinding).

Tier 3 will consist of all participants who experience an exacerbation and provide sputum, saliva, nose/throat swabs and DBS samples. We anticipate we will collect data on around 1300 exacerbations from the 804 participants.

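### The protocol does not say that a record-proven exacerbation counts when an unblinded participant has sent no form or sample, and the committee's laboratory inputs could reveal allocation

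*Protocol*

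**What the plan says.** Section 1.2.4, which justifies the primary outcome, states: "This is defined by healthcare utilisation (taking additional antibiotics and/or steroids, as recorded in the medical record, including prescription data". The sentence continues: "although we will collect symptom and treatment data from participants to infer if the event was infective". On that reading the record supplies the event, and the participant supplies evidence on its cause.

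Section 8.2.1 introduces the outcome differently: "This is defined by the clinical adjudication committee and will be based on an assessment of" four inputs. These are basic patient details, recorded treatment (in nearly the same terms as 1.2.4), "patient-reported symptoms of the AECOPD" and "laboratory results from patient-provided sputum, saliva, nose/throat swabs and DBS samples following an exacerbation". Section 1.2.2 gives the panel the task "to determine the presence or absence of the exacerbation based on several sources of information", and section 6.7 lists the same kinds of input. Section 18.7 makes the committee's determination the primary outcome data.

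For confirmation of events, 8.2.1 refers back to 8.1, where "proof of antibiotic and/or steroid prescription (e.g. GP record of medication issue), and hospital admission (e.g. a discharge letter) respectively is required". The committee's terms of reference are still to be set (8.2.1), and a charter is announced (18.7).

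Participants are told their allocation (6.5). The trial schema lets them opt out of exacerbation samples and 7.3 makes those samples subject to consent, whereas 17.3 says that everyone enrolled will have consented to them.

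**The concern.** Section 1.2.2 accepts that knowing the allocation can introduce bias and relies on blinded endpoint assessment to limit it. That protects against an assessor who favours one arm. It does not protect against evidence that reaches the assessor more or less completely according to arm. Forms and samples come from participants who know what they received. If their presence affects whether a treated episode is accepted, a difference in reporting behaviour becomes a difference in the primary rate, in either direction.

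A second route runs through the laboratory results. Section 6.7 gives the committee results from the dried blood spots (DBS). If these include anti-BCG antibody, the committee's own blinding is at risk.

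**Working it through.** **1. The definitions side by side.** Section 8.1 proof is a condition of counting under 8.2.1, so the possible cases are:

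| Record proof | Participant form and sample | 1.2.4 | 8.2.1 with 8.1 |
|---|---|---|---|
| Yes | Present and supportive | Event | Event |
| Yes | Absent or negative | Event | Not stated |
| No | Present | No event | No event |

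The sections diverge only in the middle row. That row will occur in practice: the twelve-month visit (9.7) collects a year of prescriptions and the exacerbations of the last nine months, which can bring to light treated episodes for which nothing was posted at the time.

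**2. The laboratory route.** Sections 17.4.3 and A1.3 assay exacerbation DBS for anti-BCG antibody. Section A1.1 says that these responses rise after vaccination. Section 6.7 names DBS among the results the committee looks at. No section withholds the anti-BCG part.

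**3. The plan's own sample size, reproduced.** Inputs from 14.1: rates 2.25 and 1.8 per person-year, dispersion k = 0.36, 90% power, 5% error, one year, 1:1.

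- V = 1/2.25 + 1/1.8 + 2 × 0.36 = 0.444 + 0.556 + 0.72 = 1.72
- n = (1.960 + 1.282)² × 1.72 / (ln 0.80)² ≈ 363 per group; with a pooled-rate null variance, 361.4
- 361 / 0.9 = 401.1, so 402 per group and 804 in all

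This agrees with the stated 361, 402 and 804. Nothing in this point changes the sample size.

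**4. A hypothetical scale.** The protocol gives no figure for differential counting, so the losses below are assumptions. With 361 per arm and k = 0.36, SE = √[(1/r₀ + 1/r₁ + 0.72)/361].

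- No true effect, 5% fewer events counted in the BCG arm: r₀ = 2.25, r₁ = 2.1375, SE = 0.0672, ln 0.95 / SE = −0.763. The chance of a significant result favouring BCG is Φ(−1.960 + 0.763) = 11.6%, against 2.5%.
- No true effect, 10% fewer in the BCG arm: expected ratio 0.90, chance 34.3%.
- True ratio 0.80, 5% fewer events counted in the control arm: expected ratio 0.84, power 70% instead of 90%.
- True ratio 0.80, 10% fewer in the control arm: expected ratio 0.89, power 39%.

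How missing samples might produce such losses, again hypothetically: if 25% of events in the BCG arm and 15% in the control arm lacked samples and a share q of those were rejected, the ratio under no effect would be (1 − 0.25q)/(1 − 0.15q). This is 0.97, 0.95 and 0.88 for q = 0.25, 0.5 and 1. Swapping the arms reverses the direction.

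**5. How many events may lack samples.** Section 17.5 says: "We anticipate we will collect data on around 1300 exacerbations from the 804 participants". The planning rates imply 361 × (2.25 + 1.8) = 1,462 events, or 402 × 4.05 = 1,628 with full follow-up. The ratios 1,300/1,462 = 0.89 and 1,300/1,628 = 0.80 would leave about 11% to 20% without samples. This is weak evidence: 722 × 1.8 is also about 1,300, so the figure may not be a forecast of sample return at all, and it says nothing about a difference between arms.

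**The case against.** The best defence is that 8.2.1 is closer to 1.2.4 than it first appears. It repeats the recorded-treatment criterion and brings in the 8.1 proof requirement. A reader might infer that symptoms or samples alone could create an event; the protocol rules that out. A reader might also infer that 1.2.4 restricts participant data to judging infection, but that sentence states a purpose and does not exclude others.

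Nor does any section say that a missing form or sample leads to rejection. Several lean the other way. The committee uses whatever information is available (6.7). Its aetiology categories include non-infectious events and likely infections with no organism found (8.2.2), so a negative culture does not disqualify an episode. Missing treatment data on the participant's form prompt a call or a check of the record (11.3). The charter may hold the rule. Section 17.3 also weakens the assumption that many will opt out of sampling.

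Finally, a record-based definition does not remove open-label bias, because care-seeking and prescribing also shape the record. Withholding symptoms altogether would make it harder to tell treatment for AECOPD from treatment for something else.

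These points limit the concern without removing it. None states that proof is sufficient, and a charter would still have to choose between 1.2.4 and 8.2.1. The point about symptoms stands, and the fix below allows for it.

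**Conclusion.** The inconsistency is real but narrow. Section 1.2.4 counts an event that the record proves; 8.2.1, 1.2.2 and 6.7 leave open whether the committee may reject that event when participant-supplied evidence is missing or negative. Because participants know their arm, committee blinding does not close this route. Separately, the DBS results offered to the committee could disclose allocation unless the anti-BCG results are held back.

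The size and direction of any bias are unknown. The ratios and error rates above rest on assumed differences between arms and show only that a small differential loss would matter: 5% is about a quarter of the 20% target effect. The documents do not support a claim that 11% to 20% of events will be rejected, that the rate ratio is biased towards BCG, or that the committee will in fact be unblinded. The contradiction does not depend on any of these figures. It should be settled before the three-monthly adjudication applies either reading.

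**What to change.** - Align 1.2.4, 1.2.2, 6.7 and 8.2.1 on one definition: presence and severity are decided from record-confirmed treatment for AECOPD, or admission.
- State that a missing participant form or sample is never a reason to reject a record-proven event.
- Withhold laboratory results from the presence decision. Release microbiology afterwards, for type and aetiology. Never release anti-BCG results to the committee.
- Symptoms may remain available to help separate AECOPD from other indications. If so, add a sensitivity analysis that counts every record-confirmed treated event.
- Reconcile the schema and 7.3 with 17.3 on whether exacerbation samples are optional.

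The cost is protocol and charter wording, a change in the order in which the adjudication pack is released, and one extra analysis. No new data, visits or participants are needed. Bias from unblinded treatment-seeking remains and should be acknowledged.

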8.2.2 Secondary outcomes

We will compare the following between intervention and control groups over 12 months follow up from IMP administration date (or after the date of randomisation if no treatment was administered), unless otherwise stated.

- Hospitalisation rate for infective exacerbations equivalent to the rate of severe AECOPD.
- Quality of life (QOL), as defined by the COPD Assessment Test (CAT)

- Total number of days of antibiotic therapy for AECOPD during follow up, defined by patient self-report at each event, and confirmed by the site in the medical record (section 8.1).
- Total number of days of oral steroid therapy for AECOPD during follow up, defined by patient self-report at each event, and confirmed by the site in the medical record (section 8.1).
- Type of exacerbation (as they occur (rate over time)):
 - Defined by Anthonisen criteria, collected at AECOPD using patient self-report of symptoms. Type 1 being characterised by increased breathlessness, sputum volume and sputum purulence, type 2 by two of these three symptoms and type 3 by a single symptom.
 - Defined by the clinical adjudication committee (CAC), who will use sputum, viral and symptom data to determine aetiology of each event, categorising events as infectious (confirmed bacterial, confirmed viral, clinically likely but no organism identified) and non-infectious.

8.2.2.1 Qualitative acceptability study

Themes relating to vaccine acceptance and AECOPD prevention strategies in general, as obtained by the Framework method, described in section 3.3 constitute the outcomes of the qualitative work.

9. TRIAL PROCEDURES

9.1 Patient identification and invitation to participate

Potentially eligible patients will be identified and invited to take part in the trial (section 6).

9.2 Baseline visit

Patients screening and consent will take place at the baseline visit. The baseline visit will occur faceto-face at a participating research site (either primary or secondary care site). At the start of the baseline visit, patients will have an opportunity to ask questions about the trial before being asked to provide full informed consent (section 5). Once screening is completed and consent is obtained, site staff will then complete the baseline blood sample details CRF with patients and randomise participants, perform spirometry (if required i.e. if not available within the last 12 months), and the participant will provide a blood sample, sputum sample, nasopharyngeal swab and complete a dried blood spot (DBS) test. The blood sample will be sent to the research sites local laboratory and an IGRA test will be performed (section 6.3). Participants will be shown how to complete the DBS test themselves and given a test kit to take home to complete the DBS test themselves after each exacerbation and when their three month follow up is due. Site staff will also demonstrate to the participant how to take a sputum sample and perform a nasopharyngeal swab, as participants will be asked to send these samples to the main laboratory based at the QE hospital (UoB) if/when they experience an exacerbation at home.

Trial procedures and points to be collected at are:

- · Confirmation of inclusion and exclusion criteria, excluding IGRA result
- Trial suitability
- Decliner questionnaire (if applicable)
- · Informed consent
- · Randomisation

The following baseline information will be completed:

- Demographic information including sex, ethnicity, date of birth
- Medical history & concomitant medications
- Smoking status
- Employment status
- Vaccine status
- NHS number
- Height and Weight
- Educational level
- Marital status
- COPD exacerbations
- Contact details Address, email and telephone number
- COPD Assessment Test[™] (CAT)
- Lung function test spirometry
- Blood sample
- Dried blood spot test (DBS)
- Sputum sample + nasopharyngeal swab

9.3 IGRA result

Only participants with a negative IGRA result are eligible to take part in the trial. If the participant's result is indeterminate, the research site will arrange for a repeat blood sample to be taken and IGRA test performed. If the participant's result is positive, the participant will be informed that they are not eligible to take part in the trial and referred for assessment of TB status. For those randomised to the intervention arm, a treatment visit will be arranged to take place at the participant's local administrating hub site for them to receive the BCG vaccine.

Data point to be collected:

- IGRA blood results
- Affirmation of eligibility

9.4 Administration visit

Participants allocated to the intervention arm will receive a letter inviting them to a clinic at their closest administrative hub to receive the BCG vaccine (section 7.1). The visit and so vaccine administration to the participant, should be within 6 weeks of randomisation. The administering site will request that all women of childbearing potential (WOCBP) to arrive 10 minutes before their appointment for a pregnancy test to confirm pregnancy status. We refer to WOCBP as per Clinical Trial Facilitation Group (CTFG) guidance as "fertile, following menarche and until becoming postmenopausal unless permanently sterile. Permanent sterilisation methods include hysterectomy, bilateral salpingectomy and bilateral oophorectomy. A postmenopausal state is defined as no menses for 12 months without an alternative medical cause. A high follicle stimulating hormone (FSH) level in the postmenopausal range may be used to confirm a postmenopausal state in women not using hormonal contraception or hormonal replacement therapy (HRT). However, in the absence of 12 months of amenorrhea, confirmation with more than one FSH measurement is required."

If a woman is randomised to the BCG group and found to be pregnant after randomisation but before the administration of treatment, she will not receive the trial intervention. However, she will be followed up according to the protocol, and her data will be collected.

The administrative hub pharmacy will reconstitute the allocated IMP (section 7.2) and a delegated member of staff will administer the injection (section 7.3).

Data point to be collected:

- Pregnancy test results (where applicable)
- BCG vaccine accountability details

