6.3 IGRA test results

Only patients with a negative IGRA test result from the blood sample taken at baseline are eligible to join the trial. If a participant's result is indeterminate, the site should contact the patient to ask them to provide a new sample of blood for testing. If the result of the second IGRA test is indeterminate, the patient will be deemed as ineligible. If the participants result is positive, they should be referred for assessment of TB status. Once a negative IGRA result has been received, the participant is eligible to receive the vaccine if they are allocated to the intervention arm. It is anticipated that the results from the IGRA test to be available within 1-2 days with a maximum of a week. Eligibility will be affirmed by a medically trained doctor. Patients with positive or 2 indeterminate IGRA will be informed by a letter from their recruiting site that their blood test results didn't meet the study inclusion criteria.

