6.4 Randomisation

Patients will be randomised after eligibility, excluding IGRA result, has been confirmed by a medically qualified doctor. Randomisation will be provided by the Birmingham Clinical Trials Unit (BCTU) using a secure online system (available at https://stabilise.bctu.bham.ac.uk), thereby ensuring allocation concealment.

Unique log-in usernames will be provided to those who wish to use the online EDC system and who have been delegated the role of randomising patients into the trial as detailed on the STABILISE site signature and delegation log. These unique log-in details must not be shared with other staff and in no circumstances should staff at sites access the system using another person's login details. The online trial EDC system will be available 24 hours a day, 7 days a week, apart from short periods of scheduled maintenance.

In the event of the online system not being available, a back-up telephone toll-free randomisation service ([name]) is available Monday to Friday, 09:00 to 17:00 UK time, except for bank holidays, government guided closures and University of Birmingham closed days.

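### On vaccination day the Protocol rechecks pregnancy only, although immunosuppression and high-dose prednisolone can newly arise in the up to 6 weeks before live BCG is given

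*Protocol*

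**What the plan says.** **Before randomisation.** Protocol section 6.4: "Patients will be randomised after eligibility, excluding IGRA result, has been confirmed by a medically qualified doctor". Section 9.2 lists the same step at the baseline visit: "Confirmation of inclusion and exclusion criteria, excluding IGRA result". The section 4.2 exclusions include immunosuppression as judged by the investigator (chemotherapy and disease-modifying rheumatic drugs are among the examples) and prednisolone above 20 mg a day for more than 14 days in the previous 3 months.

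**After the IGRA result.** Section 6.3 says: "Once a negative IGRA result has been received, the participant is eligible to receive the vaccine if they are allocated to the intervention arm". The result is expected "within 1-2 days with a maximum of a week". The same section adds: "Eligibility will be affirmed by a medically trained doctor". Section 9.3 records "Affirmation of eligibility" beside the IGRA result. If the first result is indeterminate, "the research site will arrange for a repeat blood sample to be taken and IGRA test performed".

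**At the dose.** Section 7.1 describes a live attenuated vaccine, given no later than 6 weeks after randomisation, with hubs that may serve three or four sites. Section 9.4 requires a pregnancy test for women of childbearing potential, and for a woman in the BCG group "found to be pregnant after randomisation but before the administration of treatment, she will not receive the trial intervention". The data items for that visit are the pregnancy result and vaccine accountability. In Table 2 (section 9.8) the vaccine column holds only the pregnancy test and BCG. The eligibility check is marked at baseline only; medical history and medications are marked at baseline and 12 months only.

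**The concern.** The two exclusions depend on time. A participant who meets neither at baseline can meet one by the day of injection. The protection matters on that day, because the vaccine is live.

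New steroid use during the wait is plausible in this population. Participants enter with at least two exacerbations in the past year, and sections 1.2.4 and 8.1 identify a moderate exacerbation by antibiotic and/or steroid treatment. The Protocol saw the same window for pregnancy: section 10.5.4 asks at baseline about plans for the next 6 weeks, and section 9.4 adds a test and a withholding rule on the day. Nothing comparable is written for the other two exclusions. Staff who follow sections 6.3 and 9.4 as written could give live BCG to someone who by then meets one of the trial's own exclusions.

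**Working it through.** The Protocol states no figure here to reproduce. The check is a reading of the text plus interval arithmetic.

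**Inputs.** Latest dose: 6 weeks = day 42 after randomisation (7.1, 9.4). Baseline check: day 0. IGRA result: day 1 or 2, at most day 7 (6.3). Shortest disqualifying steroid course: more than 14 days, so 15 days (4.2).

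**Assumptions.** The doctor affirms eligibility on the day the IGRA result arrives; neither 6.3 nor 9.3 dates it. For a repeat test, blood is drawn on the day of the first result and each test takes 7 days. The affirmation is taken, generously, to cover every criterion; its scope is not stated.

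**Gap before a day-42 dose, and earliest dose day by which a whole new 15-day course fits.** Gap = 42 − day of last check; earliest day = day of last check + 15.

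| Last check | Day | Gap to day 42 | New course fits by dose day |
|---|---|---|---|
| Baseline eligibility check | 0 | 42 | 15 |
| Affirmation, result in 1 day | 1 | 41 | 16 |
| Affirmation, result in 2 days | 2 | 40 | 17 |
| Affirmation, result in 7 days | 7 | 35 | 22 |
| Affirmation after repeat test | 14 | 28 | 29 |

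Every gap exceeds 15 days. A course already under way at the last check, but not yet past 14 days, would cross the limit sooner. The gaps are maxima: the wait may be shorter than 6 weeks, and a later affirmation would shorten the last four.

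**Can the prednisolone exclusion lapse again before day 42?** No. Three months is about 13 weeks, longer than the whole 6-week window. Any course taken after baseline is still inside the look-back on day 42. Counting the look-back from the injection day is my reading; section 4.2 is written as an entry criterion.

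**Other sections searched.** Section 7.2 asks staff to inspect the vaccine, not to recheck the participant. Section 7.4 restricts no drugs. Section 7.5 calls modification or discontinuation not applicable. Section 9.9 covers follow-up of participants found ineligible late, but does not tell the vaccinator to look. Section 11.2 lists a participant form for exacerbation symptoms and treatment, but nothing connects it to the dosing decision.

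**Scale of exposure only.** With the section 14.1 planning values (2.25 events per person-year, k = 0.36), the expected count in 6 weeks is 2.25 × 6/52 = 0.260. The chance of at least one moderate to severe exacerbation is 1 − (1 + 0.36 × 0.260)^(−1/0.36) = 0.22. At 1.42 to 2.5 events per person-year it is 0.15 to 0.24. For a 2-week wait at 2.25 it is 0.08.

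**The case against.** The best case for the Protocol is that this is an omission and not a contradiction. Section 4.2 sets entry criteria, and sections 6.4 and 9.2 apply them consistently. A doctor affirms eligibility after randomisation, possibly close to the dose. The Vaccine Administration CRF (section 11.2) is completed when the vaccine is given, and its content is not shown; it may already ask these questions. The section 9.4 list is of data items, not a clinical checklist. Pregnancy has its own reason for special treatment in section 10.5.4. The exacerbation form, and the telephone call or record check in section 11.3 when treatment data are missing, may tell the trial team of steroid use as it happens.

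Much of this stands as a limit on the claim. The point concerns the Protocol text, and the intervals after affirmation rest on an assumed date. But none of it puts a check at the point of injection, and section 6.3 names only the negative IGRA as the step that opens the way to the vaccine.

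Three stronger readings should be resisted.

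- A reader might infer that 22% of the BCG arm would become ineligible. That figure is the chance of any moderate to severe exacerbation during a full 6-week wait. The documents give no steroid dose or course length for an exacerbation and no rate of new immunosuppression.
- A reader might infer from section 7.5 that the dose cannot be withheld. Sections 9.9 and 14.2.1 foresee late ineligibility and non-receipt for any reason.
- A reader might infer that no doctor looks at eligibility after randomisation. Sections 6.3 and 9.3 say otherwise.

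**Conclusion.** The point holds as a gap in the Protocol's dosing procedure. Pregnancy is the only participant check required on the day, while a live vaccine may follow the baseline eligibility check by up to 42 days and two exclusions can newly arise in between. If affirmation coincides with the IGRA result, about 5 to 6 weeks can remain before the latest dose, or about 4 weeks after a repeat test. How many participants would be affected cannot be estimated, and the actual wait is not given.

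This is a patient-safety improvement that is cheap to make. It does not threaten the validity of the primary comparison: the Protocol already follows up and analyses participants who do not receive the vaccine.

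**What to change.** Add to section 9.4, with a matching entry in the vaccine column of Table 2:

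> On the day of vaccination and before reconstitution, staff will ask about new immunosuppression (illness or treatment) and about prednisolone above the section 4.2 limit in the 3 months before that day, and will record the answers on the Vaccine Administration CRF. A positive answer is referred to the investigator or a delegated doctor. If an exclusion is met, the vaccine is withheld and the participant is followed up and analysed as randomised.

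Referral is needed because section 4.2 leaves immunosuppression to the investigator's judgement. Follow-up after withholding mirrors the pregnancy rule in 9.4 and fits 9.9 and 14.2.1; section 8.2.1 already starts the clock at randomisation when no vaccine is given. Do not offer deferral for prednisolone, since a new course cannot leave the look-back by day 42. Leave section 7.4.3 as it is, so that steroids remain unrestricted during follow-up. State also the scope and timing of the doctor's affirmation in 6.3 and 9.3.

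**Cost.** A few lines of text, one table entry, a few items on an existing form at an existing visit, and a doctor who can be reached during the clinic. Checking before reconstitution limits waste of multi-dose vials. The downside is a few more treatment non-receivers in the BCG arm, which slightly dilutes the treatment-policy effect.
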